## 9.0 AGENT INFORMATION

### 9.1 **Drug Name**

Propranolol (Inderal, Inderal LA, Innopran XL)

#### 9.1.1 Structure

Propranolol hydrochloride (2-Propanol, 1-[(1-methylethyl)amino]-3-(1-naphthalenyl)-, hydrochloride is a synthetic, nonselective antagonist of beta-adrenergic receptors. It has been used extensively in pediatrics for more than 40 years, principally for cardiac indications (e.g. supraventricular tachycardias) but more recently for other indications. In particular, broad experience with propranolol for the treatment of pediatric hemangiomas has recently emerged, after the initial serendipitous observation of its efficacy in this condition[30].

9.1.2. Supplied by: Commercially available

9.1.3. Formulation  
Commercially available.

9.1.4. Storage  
Patients will obtain propranolol from commercial pharmacy.

9.1.5. Solution Preparation  
N/A.

9.1.6. Administration  
Propranolol will be administered orally, either as a tablet or as a suspension, in equal divided doses two times a day.

For children (12-18 years of age): Parents will be informed of the signs of hypoglycemia, hypotension, and bradycardia.

9.1.7. Toxicities  
A list of those adverse events encountered in treatment of infantile hemangioma is included below with estimates of overall frequency provided in the recent review by Drolet et al.[19]. Because infantile hemangiomas are vascular anomalies of childhood, like lymphatic malformations, we believe these may best represent adverse events that would affect the patients in our study.

Table 7. Known toxicities of propranolol

Known Toxicities	Frequency
Sleep disturbance	3.7%
Asymptomatic hypotension	2.8%
Somnolence	2.2%
Bronchopulmonary symptoms (wheezing, breathing disturbance)	1.9%
Cool or mottled extremities	1.7%
Asymptomatic bradycardia	0.9%
Hypoglycemia	0.9%
Diarrhea	0.8%
Gastroesophageal reflux	0.7%

Detailed pharmacologic data is available on the FDA website:  
[http://www.accessdata.fda.gov/drugsatfda\\_docs/label/2011/016418s080,016762s017,017683s008lbl.pdf](http://www.accessdata.fda.gov/drugsatfda_docs/label/2011/016418s080,016762s017,017683s008lbl.pdf).

## **10.0 CRITERIA FOR REMOVAL FROM PROTOCOL THERAPY AND OFF STUDY CRITERIA**

10.1 **Criteria for Removal from Protocol Therapy**

- Intercurrent illness that prevents further administration of treatment.
- Adverse Events requiring removal from study (See Section 6.0).
- Refusal of further protocol therapy by patient/parent/guardian

- d) Non-compliance that in the opinion of the investigator does not allow for ongoing participation.
- e) Completion of 2 months of therapy.
- f) Physician determines it is not in the patient's best interest.

Patients who are off protocol therapy are to be followed until they meet the criteria for Off Study (see below). Ongoing adverse events, or adverse events that emerge after the patient is removed from protocol therapy, but within 30 days of the last dose of investigational agent, must be followed until resolution or stabilization of the adverse event. Follow-up data will be required unless consent is withdrawn.

## 10.2 Off Study Criteria

- a) Completion of 10 months of follow-up after the last dose of the investigational agent.
- b) Death
- c) Lost to follow-up
- d) Withdrawal of consent for any further data submission
- e) Enrollment onto another anti-lymphatic malformation study

# 11.0 STATISTICAL AND ETHICAL CONSIDERATIONS

## 11.1 Sample Size and Study Duration

**Sample Size:** Based on our current clinical volume, we anticipate a total enrollment of 15-20 (this is just an example to show a range) patients over a period of 24 months.

**Accrual Rate:** We anticipate that 8-10 patients per year will be accrued to the study.

**Accrual Targets:** LMs affect the general population without known differences in genders or ethnicities. Therefore, we expect accrual to reflect the makeup of the population in the region(s) surrounding our institution.

## 11.2 Study Design/ Endpoints (Table 2)

11.2.1 **Study design:** Each patient will serve as his/her own control, for comparison of study questionnaires (subjective) and with changes in the clinical measurements and imaging measurements of the anatomic area affected by lymphatic malformation compared before and after treatment (objective). In our experience, children exhibiting responses to propranolol displayed these within 2 weeks of beginning propranolol treatment, with estimated reduction in the overall volume of the affected area exceeding 20%.

11.2.2 **Primary endpoints:** The primary endpoint will be the tolerability of escalating dosage of propranolol both by subjective reporting (survey instrument) as well as objective measurements of vital signs. Survey instruments include a general quality of life (QOL) and function survey (SF-36), as well as validated survey instruments for patients with lymphedema (LYMPH—ICF, LYMPH—LCF—LL)[38, 39].

11.2.3 **Secondary endpoints:** The secondary endpoints of the study will be both subjective and objective evaluation of the lymphedema after propranolol treatment, as measured by both survey instrument and objective measurements (clinical exam and radiological studies), as well as biological assays from tissues obtained from biopsies.

11.2.3.1 We will determine whether higher doses of propranolol are well tolerated in this patient population. Secondarily, we will measure determine whether higher doses correlate with improvement in lymphedema symptoms and signs, and healing or improvement of skin lesions, if present (reduced lymphatic leakage, reduced bleeding). Skin lesions will be photographed at clinical visits, and daily lymphatic fluid losses estimated by weight measurements.

Using MRI and body composition analysis, we will determine whether propranolol decreases lymphedema, alters edema water content and location (intracellular vs. interstitial), or alters adiposity of affected extremity.

We will study the biologic activity of oral propranolol against lymphedema, by examining the expression of progenitor cell markers, lymphatic endothelial cell markers, beta-adrenergic receptor expression, macrophage markers and detection of adipocyte content of biopsy specimens (see table below). Results will be compared to ultrasound and magnetic imaging data.

### 11.3 Analysis of Secondary Endpoints

#### 11.3.1 Biomarkers

In the context of this study, we plan to perform immunohistochemical studies to assess alterations in lymphatic vessel/channel formation, adipocyte differentiation, and changes in inflammation. We have selected markers that we have previously shown to be altered by propranolol either in isolated LMPCs in culture or in the mouse model (*unpublished*). Expression of the beta-adrenergic receptors will be assessed as propranolol is a pan-beta-adrenergic receptor antagonist. To date, no molecular markers have been identified to correlate with LM patient improvement. Identification of such markers could provide an important benefit to affected patients. Morphological changes in the lymphatic vasculature will also be quantified using ImageJ software. Student's T-test will be employed to determine significance, with  $p < 0.05$  considered significant.

**Table 3. Markers to be probed and assessed in blood and tissues**

Progenitor cell markers	CD133, CD45, podoplanin, CD90, NG2
Lymphatic endothelial cell markers	VEGFR-2, VEGFR-3, podoplanin, Prox1, LYVE1
Beta-adrenergic receptors	Beta-1, beta-2, beta-3 adrenergic receptors
Macrophage markers	CD68, iNOS, F4/80

The analyses we plan to perform on the specimens have been validated by our laboratory using discarded de-identified specimens[14]. Fixed frozen tissue will be prepared and 5-micron sections generated. Standard immunohistochemistry will be performed with commercially available antibodies and H&E staining performed. Results will be captured by microscopy and digital camera. Results will be quantified using ImageJ software and *Student's t-test* to determine significance, with a  $p < 0.05$  considered significant. We have already isolated similar specimens from  $> 10$  patients and have obtained consistent results using these methodologies.

We have comprehensive data on *in vitro* and *in vivo* analysis of 12 cell lines from patients with LMs. We have demonstrated consistently that LMPCs have unique characteristics by FACS analysis and gene expression profile analysis. They express mesenchymal stem cell markers CD90 and NG2, and can be differentiated into various terminal cell types including adipocytes, mural and endothelial cells. When implanted into immunocompromised mice, these LMPCs formed cystic structures that phenocopy lymphatic malformations. These features are reproducible between LMPC cell lines, and demonstrate consistent changes in gene and protein expression after treatment with propranolol.

We are expecting to recruit 20 patients into this study. Our assays are sufficiently sensitive to detect 5-10% differences in proliferation rate and gene and protein expression changes.

#### 11.3.2 Imaging Studies

Lymphedema MRI characteristics before and after propranolol therapy will be assessed and related to clinical outcome, as applicable. Specifically, whole body MRI will be used to evaluate body composition and changes in regional adipose tissue depots in the affected limb[21-23].

Furthermore, changes in body composition (water and fat content) in response to propranolol treatment will be evaluated in this study. To evaluate water content, the standard deuterium dilution technique will be used. Fasting patients will have blood draw before drinking stable deuterium isotopes and sodium bromide and after isotope equilibration (about 3-4 hours). Total body water, extra-cellular and intracellular water content can be calculated[22, 40]. Furthermore, a quantitative magnetic resonance (QMR) system will be used to evaluate body (fat and water) content in response to propranolol treatment[21]. Quantification and analysis of results will be performed by [name].

#### 11.3.3 Patient-Reported Outcomes; Symptom Assessment etc.

Patients' self-reported tolerance to propranolol will be assessed using validated quality of life (QOL) health surveys (SF-36, Lymph-ICF, Lymph-ICF-LL) SF-36 is an accepted general health status survey[38, 39]. Lymph-ICF and Lymph-ICF-LL are validated, disease-specific survey instruments for patients with lymphedema that evaluate physical and mental activity, impairments in function and activity limitations related to lymphedema.

#### 11.3.4 Genetic analysis

Primary lymphedema has been shown to be associated with genetic mutations. There is a mutation in flt4 (vegfr3) gene in Milroy's[8]. More recently, somatic mutations have been identified in another subset of patients with lymphatic malformations[36, 37]. Patient blood and tissues will also be sequenced using Next-Gen exome sequencing analyses to probe for *de novo* genetic mutations and screening for mutations in genes known to be associated with lymphedema (vegfr3, pik3ca) and correlated with treatment response to propranolol. Columbia University has core facilities available for these analyses. As these tests are performed under experimental and not clinical indications, individual results will not be shared with study subjects. However, once the studies are published, the published aggregate results can be made available to study subjects.

#### 11.4 **Ethical Considerations**

Patients with LMs of the extremities may experience a range of complications, including pain, bleeding, infections, and functional limitation. These can result in a severe lifelong burden of disease, exacerbated by the social difficulties imposed by physical differences and school absence caused by acute illness. No validated medical therapies currently exist. Surgical and interventional treatments can improve and palliate disease, but are rarely curative. The identification of effective treatments for these patients is therefore urgent.

The recent development in our lab of model LMs *in vivo* and *in vitro* has provided a rational basis for identifying potential new therapeutic agents[14]. Our *in vitro* and *in vivo* studies are consistent with recent reports of propranolol efficacy in small groups of patients[15-18], and with our initial clinical experience. The systematic study of propranolol, which has a favorable risk profile in patients and a biologic basis for efficacy in pediatric patients with lymphatic malformations, would thus appear ethically justified.

#### 11.5 **Reporting and Exclusions**

All of the patients who met the eligibility criteria (except those who received no propranolol) will be included in the main analysis of the response. All conclusions will be based on all eligible patients.

Sub-analyses may then be performed on the basis of a subset of patients, excluding those for whom major protocol deviations have been identified. However, these sub-analyses will not serve as the basis for drawing conclusions concerning treatment efficacy, and the reasons for excluding patients from the analysis will be clearly reported.

#### 11.6 **Inclusion of Children, Women and Minorities**

Children ( $\geq 12$  years) and adults of both gender and of all races and ethnic groups are eligible for this trial.

### **12.0 EVALUATION CRITERIA**

#### 12.1 **Adverse Events**

Any patient who receives the study drug will be evaluable for Adverse Effects. This study will utilize the NIH Common Terminology Criteria for Adverse Events v4.0 (CTCAE) for evaluating adverse events.

#### 12.2 **Disease Parameters**

Measurable disease: Measurable lesions are defined as those that can be accurately measured in at least one dimension (longest diameter to be recorded) as  $> 50$  mm by clinical exam and MRI. All measurements must be recorded in millimeters (or decimal fractions of centimeters).

#### 12.3 **Methods for Evaluation of Measurable Disease**

All measurements should be taken and recorded in metric notation using a ruler, measuring tape, or calipers. All baseline evaluations should be performed as closely as possible to the beginning of treatment.

The same method of assessment and the same technique should be used to characterize

each identified and reported lesion at baseline and during follow-up.

Clinical lesions: The circumference of the affected (vs. unaffected) extremity will be documented in the patient's clinical chart along pre-determined landmarks), as this is a standard part of care for patients with extremity LM. Landmarks include: midway point between ASIS (anterior superior iliac spine) to the patella for the thigh, and midway point between patella to the medial malleolus for lower extremities. The midway point between the axillary crease to medial epicondyle (upper arm) and midway point between medial epicondyle to hamate bone of the wrist (forearm) for upper extremities.

MRI and QMR have excellent contrast, spatial, and temporal resolution. The same scanner should be used and the image acquisition protocol should be followed as closely as possible to prior scans. While CT scans may give even improved spatial resolution, MRI has the advantage of no ionizing radiation, gives superior soft tissue resolution, and allows for multi-planar imaging.

#### 12.4 **Response**

Patients should be re-evaluated for response by clinical examination every 2 weeks. Baseline MRI will be obtained, and an MRI repeated at 8 weeks. Response will be evaluated in this study using quality of life survey instruments, physical examination and radiologic studies (MRI at baseline and 8 weeks).

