**Study Exemption from IND Requirements per 21 CFR 312.2(b) is pending**

## ABSTRACT

Lymphatic malformations (LMs) arise from abnormal development of lymphatic vasculature. Associated morbidity can be severe, including bleeding, sepsis, airway and visual axis obstruction (cervicofacial LMs), respiratory compromise (thoracic LMs), ascites and malabsorption (peritoneal/pelvic LMs), and limitations on mobility (extremity LMs). Severe symptoms can be life-threatening. Treatment options are often palliative and recurrence is common [1, 2]. Recently, results in our laboratory demonstrated that propranolol, a pan beta-adrenergic receptor ( $\beta$ BAR) antagonist, had cytotoxic and anti-proliferative effects against cells isolated from LM tissues. Preliminary results from treating symptomatic LM patients at our institution with propranolol at a dose range from 0.7-1mg/kg/day demonstrated a 70% positive response rate, with patients reporting improvement in their symptoms.

Despite severe morbidities and even mortality, there are no effective, objective, repeatable diagnostic tools to evaluate lymphedema severity, and there is no FDA-approved medical treatment for this devastating condition. Thus, we hypothesize that quantitative magnetic resonance (QMR) can accurately and quickly evaluate lymphedema severity, and propranolol will be effective in improving lymphedema, using QMR as a treatment response evaluator.

QMR has been validated in obesity research but has never been validated for lymphedema. It has the ability to quantify total body water, extracellular and intracellular water. Lymphedema results when there is excess, pathological accumulation of fluid in the interstitial spaces (extracellular water). Therefore, QMR has the potential to sensitively and accurately quantify the severity of extracellular water accumulation, thus severity of lymphedema.

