### 1.2 Secondary Aims

- 1.2.1 to assess disease-specific lymphedema patients’ response to propranolol
- 1.2.1a to assess *subjective* patient-reported lymphedema-related symptoms
  - i) Validated questionnaires: LYMPH—ICF, LYMPH—ICF--LL
- 1.2.1b to assess *objective* measures
  - i) Physical examination: Weight, BMI, limb girth discrepancy
  - ii) Imaging evaluation: MRI
  - iii) Blood and tissue analysis: circulating and tissue biomarkers
  - iv) Genetic analysis: correlation of somatic mutations to propranolol response

Table 2. Primary and secondary endpoints

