## 2.0 BACKGROUND

	Primary Endpoint (Aim 1)	Secondary Endpoint (Aim 2)
Subjective Assessment	Questionnaires QOL	Questionnaires
	Short Form 36 Lymph-ICF Lymph-ICF-LL	Symptoms (Drainage, pain) Activity levels Clothing size change
Objective Assessment	Clinical and radiological Exam	Clinical and radiological Exam
	Blood pressure Heart rate Blood sugar Whole Body MRI QMR Deuterium and NaBr	Weight, BMI Limb girth discrepancy CTCAE Grading for Lymphedema Imaging: QMR, whole body MRI Blood and Tissues Circulation biomarkers IHC lymphatic vessel phenotype PIK3CA mutational analysis Next Gen sequencing analysis

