## 8.4 Statistical Analysis

Descriptive statistics will be used to summarize patient characteristics, toxicity data, response data and biomarker expression. Toxicity rates at each dose tested will be presented with 95% exact confidence intervals. Responses will be evaluated among patients treated at the highest tolerable dose. Continuous outcomes will be summarized using mean  $\pm$  standard deviation or median (interquartile range) for non-normal data. Comparisons between groups and response changes from baseline will be evaluated using two-sided t-tests or the non-parametric equivalent Wilcoxon Rank-Sum test (for non-normal data). Association between PIK3CA mutational status and patient response will be assessed using chi-square/Fisher exact test. All analyses will be performed using a type I error of 0.05. Biostatistics will be done using Irving Institute for Clinical and Translational Research statistical services at Columbia University Medical Center.

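### Efficacy is secondary, but the plan intends efficacy conclusions without naming the response measure that decides them, and it tests every candidate at 0.05

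*Combined protocol and SAP*

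**What the plan says.** Efficacy is secondary. Section 11.2.2 makes tolerability the primary endpoint (the abstract and section 1.1 add validation of QMR), and section 11.2.3 groups all lymphedema response measures as secondary.

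The plan nevertheless states an efficacy hypothesis. The abstract says that "propranolol will be effective in improving lymphedema, using QMR as a treatment response evaluator". Section 11.2.3.1 says that, using MRI and body composition, "we will determine whether propranolol decreases lymphedema, alters edema water content and location (intracellular vs. interstitial), or alters adiposity of affected extremity". Section 11.5 bases all conclusions on all eligible patients and discusses which analyses may support conclusions about efficacy.

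The measures are listed in several places, and none is ranked:

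- Section 12.4: "Response will be evaluated in this study using quality of life survey instruments, physical examination and radiologic studies (MRI at baseline and 8 weeks").
- Section 1.2: "Validated questionnaires: LYMPH—ICF, LYMPH—ICF--LL" and "Physical examination: Weight, BMI, limb girth discrepancy", plus MRI.
- Table 2, secondary column: "Imaging: QMR, whole body MRI", with symptoms, activity, clothing size and a CTCAE lymphedema grade.
- Section 11.3.2: MRI adipose depots, QMR fat and water, and total, extracellular and intracellular water by dilution.

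Section 12.4.1 says who is evaluable but gives no threshold or rule for a response. Section 8.4 says that "response changes from baseline will be evaluated using two-sided t-tests or the non-parametric equivalent Wilcoxon Rank-Sum test (for non-normal data") and that "All analyses will be performed using a type I error of 0.05". The document contains no hierarchy, no multiplicity adjustment and no exploratory label for these tests.

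**The concern.** The candidate measures can disagree. A questionnaire may improve while extracellular water does not move, or weight may fall with no change in girth discrepancy. As written, a favourable result on any of them could be offered as the answer to whether propranolol decreases lymphedema, and the choice could be made after the results are seen. The 0.05 in section 8.4 is then the error rate of each test, not of the efficacy conclusion.

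The gap also carries forward. Section 8.4 relates PIK3CA status to patient response by a chi-square or Fisher test, which needs a definition of response that the plan does not give.

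**Working it through.** **The plan's own figure.** Section 11.1 expects 15-20 patients over 24 months at 8-10 per year. 8 × 2 = 16 and 10 × 2 = 20, so the figure reproduces to within one patient at the lower end. It is accrual arithmetic only. No power, effect size or family-wise error rate is stated, so there is no such figure to check.

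**Inputs from the documents**

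- Alpha: 0.05 per analysis, two-sided (8.4), which is 0.025 in the improving direction.
- Sample size: 15 to 20 (11.1).
- Timing: baseline against end of treatment. Section 11.2.1 compares before with after treatment, 12.4.1 ties subjective evaluation to baseline and the last visit, and Table 6 schedules MRI, QMR and body water only pre-study and at Week 8.

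**Assumed number of tests.** The documents do not fix this. Two counts bracket a fair reading:

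- Seven: SF-36, the two Lymph-ICF versions as one, weight, BMI, girth discrepancy, MRI, QMR.
- Ten: Lymph-ICF, Lymph-ICF-LL, weight, girth discrepancy, MRI regional adipose tissue, QMR water, QMR fat, and total, extracellular and intracellular water. BMI is left out as a near-duplicate of weight.

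**Assumed correlation between changes.** The documents give none, so 0, 0.5 and 0.8 are shown.

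**Formula for independent tests.** The chance of at least one significant change is 1 − 0.95^K, and of at least one false improvement 1 − 0.975^K.

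- K = 7: 1 − 0.95^7 = 30.2%; 1 − 0.975^7 = 16.2%.
- K = 10: 1 − 0.95^10 = 40.1%; 1 − 0.975^10 = 22.4%.

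**Correlated tests.** These were simulated as one-sample two-sided t-tests on change scores with zero true mean, equal correlation between all measures, n = 20 and 40,000 runs per setting:

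| Tests | Correlation | Any significant change | At least one false improvement |
|---|---|---|---|
| 7 | 0 | 30% | 16% |
| 7 | 0.5 | 24% | 12% |
| 7 | 0.8 | 15% | 8% |
| 10 | 0 | 40% | 22% |
| 10 | 0.5 | 29% | 15% |
| 10 | 0.8 | 18% | 9% |

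At n = 15 every entry is within about one percentage point.

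**Comparison.** One pre-named test has a 5% chance of a false significant change and a 2.5% chance of a false improvement. The range of 8% to 22% for false improvement is about 3 to 9 times 2.5%.

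**After the fix.** One named contrast restores 5% two-sided. Holm across the listed measures keeps the family-wise error at or below 5%, with a strictest step of 0.05/7 = 0.0071 or 0.05/10 = 0.005.

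**The case against.** The strongest reply is that these are openly secondary endpoints in a 15-20 patient single-arm study. Section 8.4 opens with descriptive summaries, the plan never claims a 5% family-wise rate, and ranking secondary measures is good practice rather than an obligation. That stands as a limit on severity. It does not remove the point, because sections 11.2.3.1 and 11.5 go beyond description.

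Four stronger readings are tempting, and the documents do not support them:

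- A reader might infer that an inert drug has roughly a 30% chance of a false response. That figure counts significant worsening as response. At ten tests and correlation 0.5, false improvement is about 15%.
- A reader might take the two-weekly clinical re-evaluation in section 12.4 as further tests at Weeks 2, 4 and 6. Testing those visits would raise the error, but the text does not plan it. Sections 11.2.1 and 12.4.1 point to before against after and to the last visit. The open question is the measure more than the visit.
- A reader might conclude that section 12.4 removes QMR as a response measure. Section 12.3 treats MRI and QMR together as evaluation methods, and Table 2 lists QMR among the secondary imaging. The inconsistency is one of naming and ranking.
- A count of ten can be called generous. Lymph-ICF-LL is the lower-limb version, so a patient may contribute mainly one of the two questionnaires, and total water is the sum of its two compartments. This is fair, and it is why the range starts at seven. The count could also be larger, since symptoms, the CTCAE grade and questionnaire subscales are left out.

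**Conclusion.** The point holds, as a cheap improvement. Efficacy is secondary, but the plan states an efficacy hypothesis, intends conclusions on it, and does not say which response measure decides. The abstract and section 12.4 name different evaluators, other sections add more, and section 8.4 gives each test the full 0.05.

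With no true change and 15 to 20 patients, the chance of at least one significant change in either direction is about 15% to 40%. The chance of at least one false improvement is about 8% to 22%, and 12% to 15% at correlation 0.5, against 2.5% for a single test. These figures rest on 7 to 10 baseline-to-Week 8 tests, equal correlations from 0 to 0.8, normally distributed changes and a paired analysis. The count and the correlations are assumptions, so the range should be quoted and not a single number.

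The calculation also takes the true mean change as zero. Without a control arm, regression to the mean or the supportive care continued under section 7.3 could produce apparent improvement, and controlling multiplicity would not prevent that.

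**What to change.** Before any Week 8 response data are analysed, amend sections 8.4, 11.2.3 and 12.4 as follows:

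1. Name one deciding baseline-to-Week 8 contrast from data already scheduled, tested two-sided at 0.05. Examples are QMR water, which would match the abstract, or the affected-minus-unaffected girth discrepancy averaged over the two section 12.3 landmarks of the limb. The girth option needs the averaging rule, because section 12.3 gives two landmarks per limb and no way to combine them.
2. State one analysis set for it. Section 8.4 evaluates response in patients on the highest tolerable dose, while section 11.5 uses all eligible patients who received propranolol. These must be reconciled, and section 11.5 already bases conclusions on the latter.
3. Label every other response measure and every earlier visit as supportive, reported as mean change with 95% CI and no claim of significance. If the sponsor prefers not to choose one measure, list the Week 8 measures and apply Holm's procedure across them.
4. Align the abstract and section 12.4 with the choice.

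The cost is wording only, with no new patients, visits or data. A lone p < 0.05 on another measure could no longer be claimed as proof of response. Holm costs more power. At 15 patients, the standardized mean change detectable with 80% power is about 0.78 at 0.05 and about 1.05 at 0.0071, the strictest step for seven measures.
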